12.1 Adverse Events

Adverse events will be coded using the MedDRA dictionary. Levels of classification will include primary system organ class and preferred term. In addition, toxicity grading will be assigned according to NCI CTCAE.

General Rules for summarizing AEs:

- (1) An AE will be considered as treatment-emergent (TE) if it begins on or after study drug dosing, starts prior to dosing and increases in grade/severity or seriousness after dosing, or starts prior to dosing but the causality changed to “related” after dosing. In case of missing dates, an AE will be considered as treatment-emergent.

- (2) In the event of multiple adverse events being reported by the same patient, the most serious causality (related > not related) will be chosen.
- (3) In the event of multiple occurrences of the same adverse events being reported by the same patient, the maximum intensity (Grade 5 > Grade 4 > Grade 3 > Grade 2 > Grade 1 > missing > not applicable) and the most serious causality (related) will be chosen.
- (4) If a patient experiences the same AE (i.e. same preferred term) more than once, they are only counted once under the count for preferred term.
- (5) If a patient experiences more than one AE in a particular system organ class, they will only be included once in the count for the system organ class, but will appear in the count for each appropriate preferred term within the system organ class (unless it is the same preferred term).
- (6) AEs related to study drug tables include only those AEs with a relationship to study drug of 'related' or if there is a missing relationship on the AE page of the CRF.
- (7) For AE severity the following rules will be applied in determining the counts of AEs:
 - An individual patient who experiences two AEs of the same preferred term of the same severity will be included once in the appropriate severity count for the particular AE.
 - An individual patient who experiences two AEs of the same preferred term but different severity will be included once in the severity count for the higher severity but not in the count for the lesser severity.
 - In the total counts for each severity classification, an individual patient who experiences two AEs of different preferred term of the same severity will be included once in the total for the appropriate severity.
 - In the total counts for each severity classification, an individual patient who experiences two AEs of different preferred term of different severities will be included once in the total for each of the appropriate severities.

Tabular summaries will be presented for each cohort and overall for expansion phase. Summaries will include the number and percentage of patients and classified by primary system organ class and preferred term. The following summaries will be reported for AEs, TEAE regardless of drug relationship, TEAE related to study drug, TEAE grade 3 and above regardless of drug relationship, TEAE grade 3 and above related to study drug, serious AEs (SAEs), AE leading to study drug discontinuation, and AE leading to death:

- Overall summary of adverse events will descriptively summarize all adverse events, treatment-emergent adverse events (TEAE), serious adverse events (SAEs), TEAE related to study drug, TEAE with CTCAE grade 3 and above, TEAE related to study drug with CTCAE grade 3 and above, TEAE leading to death, TEAE related to study drug leading to death, TEAE related to study drug leading to discontinuation, and TEAE related to study drug leading to dose adjustment (interruption or decrease).
- Summary of TEAE by system organ class (SOC) and preferred term (PT) by decreasing frequency.
- Summary of TEAE by CTCAE grade, SOC and PT, by decreasing frequency.

- Summary of TEAE related to study drug by SOC and PT, by decreasing frequency.
- Summary of TEAE by CTCAE grade 3 and above, SOC and PT, by decreasing frequency.
- Summary of TEAE related to study drug by CTCAE grade 3 and above, SOC and PT, by decreasing frequency.
- Summary of TEAE related to study drug leading to dose adjustment (interruption or decreased), discontinuation and death by SOC and PT, by decreasing frequency.
- Summary of TEAE related to study drug leading to discontinuation and death by SOC and PT, by decreasing frequency.
- Summary of SAE by SOC and PT, by decreasing frequency.
- Summary of SAE related to study drug by SOC and PT, by decreasing frequency.

Listings of all AEs/TEAEs/SAEs will be presented by treatment group and sorted by patient id, start time, primary system organ class, preferred term and verbatim text for all adverse events recorded during the study, onset day relative to the first treatment date of AEs, date of Resolution, AEs, SAEs, related to study drug.

Listing of AE leading to study drug discontinuation and death will be presented in each study period and treatment group.

12.2 Clinical Laboratory Evaluations

Scheduled clinical safety laboratory parameters will be summarized. Absolute laboratory values will be summarized by visit. Maximum and minimum change from baseline laboratory data will be summarized. Baseline will be the last measurement taken prior to the first study drug administration of MM-398. Frequency and percent of abnormal laboratory values will be assessed. Shift to most severe toxicity grade will be summarized. These include:

- **Hematology:** hemoglobin, hematocrit, leukocytes, differential white blood cell count, absolute neutrophil count, platelets.
- **Chemistry:** sodium, potassium, chloride, bicarbonate, alkaline phosphatase, ALT (SGPT), AST (SGOT), uric acid, blood urea nitrogen, creatinine, LDH, glucose (random), calcium, magnesium, phosphate, total bilirubin, direct bilirubin, total protein, albumin.
- **Urinalysis:** A urinalysis will include descriptions of color and clarity; pH; specific gravity; and analyses of blood, glucose, ketones and total protein. A microscopic examination of the urine, to include WBC, RBC, bacteria and casts will be performed if the urinalysis is abnormal.

Abnormal lab values will be classified as low (lower than normal limit), normal (within normal range) and high (> upper normal limit). Laboratory values will also be assessed according to NCI CTCAE Version 4.0 or higher, where possible. Abnormal lab values will be flagged (Low [L],

High, [H], abnormal clinically significant [C],) where applicable in the listing. Any unscheduled laboratory assessments will be flagged [U] in the listing.

In addition, a separate listing will be created for all grade 3 and higher post-baseline laboratory observations and any out-of-range values that are identified by the investigator as being clinically significant.

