7 GENERAL STATISTICAL METHODS

7.1 General Methodology

Categorical/qualitative data will be summarized using the number of non-missing observations, frequency counts and percentages. All percentages will be presented as one-decimal point, unless otherwise specified. Percentages equal to 100 will be presented as 100% and percentages will not be presented for zero frequencies.

For continuous variables, descriptive statistics will include the number of non-missing observations (n), mean, standard deviation, median, minimum and maximum. Missing data will be counted but not included in percentage calculations. Where applicable, the same number of decimal places as in the raw data will be presented when reporting minimum and maximum, 1 more decimal place than in the raw data will be presented when reporting mean and median, and standard deviation.

Unless otherwise specified, patients will be counted only once in each tabular summary (e.g. each parameter & visit combination). Reported data that are excluded from tables, e.g. patients excluded from the corresponding analysis population or extraneous measurements (e.g. repeat assessments), will be included in the patient listings.

The pre-treatment period is the time from informed consent to the date of first study drug administration of ferumoxytol or MM-398 respectively. On-treatment period for ferumoxytol is defined as time from ferumoxytol treatment administration to prior to MM-398 administration or within 30 days from date of ferumoxytol termination if patient didn't receive MM-398. The on-treatment period for MM-398 is defined as time from the first administration of MM-398 to 30

days after date of MM-398 termination. Observations recorded on the same date of the first administration of study drug will be considered as on-treatment, unless otherwise indicated by collection time. The post-treatment period is the time following 30 days after the last administration of study drug.

In general, the patient listings will be sorted by phase, patient number and assessment date (and time) if applicable.

For patients who received study drug the reference start date (RFSTDT) is the date of MM-398 administration. Study day is computed as:

- (event/visit date - RFSTDT), if event/visit date < RFSTDT
- (event/visit date - RFSTDT+1), if event/visit date ≥ RFSTDT.

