7.6 Definitions and General Terminology

7.6.1 Baseline

- **Baseline for Ferumoxytol Safety Period**

Baseline for the ferumoxytol period is the last observation before the administration of ferumoxytol.

- **Baseline for MM-398 Safety Period**

Baseline for the MM-398 safety period is the last observation before the first administration of MM-398.

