7.6.3 Study Periods

For the evaluation of safety, assessments will be assigned to study periods. These will be:

- Ferumoxytol safety period: from time of the first dose of ferumoxytol to the time of the first dose of MM-398. If an observation contains a date only, then the corresponding ferumoxytol safety period is the time from the date of the first dose of ferumoxytol to the day before the date of the first administration of MM-398. If the patient does not receive MM-398, the ferumoxytol safety period ends at 30 days after the date of the ferumoxytol dose.
- MM-398 safety period: from time of the first dose of MM-398 to 30 days after the date of the last study drug administration of MM-398. If an observation contains a date only, then the corresponding MM-398 safety period begins on the date of the first administration of MM-398.
- Events/observations will be assigned to study periods based on the start date or date and time if time is available.

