12 SAFETY ANALYSES

Safety analyses will be based on safety population.

The analysis of safety assessments in this study will include summaries following categories of safety and tolerability data collected for each patient:

- Adverse Events
 - AEs and SAEs
 - AEs leading to discontinuation of study drug
 - TEAE
 - Deaths
- Clinical Laboratory Investigations
- Vital signs
- ECG Investigations
- Pregnancies (if any reported)
- Physical exam

Safety analyses will be presented for each safety population in accordance with the respective study periods (see Section 7.6.3). Safety analyses will be summarized by each cohort and overall for expansion phase.

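### SAP 12.2 fixes one laboratory baseline, the last value before MM-398, without limiting it to the MM-398 period, so scheduled laboratory change and shift in the ferumoxytol period come out zero or undefined

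*SAP*

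**What the plan says.** SAP 7.6.1 (Baseline) defines two safety baselines. For the imaging agent, "Baseline for the ferumoxytol period is the last observation before the administration of ferumoxytol". For the study treatment, "Baseline for the MM-398 safety period is the last observation before the first administration of MM-398".

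SAP 7.6.3 (Study Periods) sets the matching windows. The first is "Ferumoxytol safety period: from time of the first dose of ferumoxytol to the time of the first dose of MM-398", with a fallback: "If the patient does not receive MM-398, the ferumoxytol safety period ends at 30 days after the date of the ferumoxytol dose".

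SAP 12 (Safety Analyses) includes clinical laboratory data among the safety data and says "Safety analyses will be presented for each safety population in accordance with the respective study periods". SAP 6 adds that the two safety populations are analysed separately if they differ.

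SAP 12.2 (Clinical Laboratory Evaluations) plans absolute values by visit, maximum and minimum change from baseline, abnormality frequencies, shift to the worst toxicity grade, and a listing of grade 3 or higher post-baseline values plus out-of-range values that the investigator judges clinically significant. It names one baseline for all of this: "Baseline will be the last measurement taken prior to the first study drug administration of MM-398". Protocol 10.7 contains the same sentence.

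SAP 7.1 (General Methodology) has a same-day rule: "Observations recorded on the same date of the first administration of study drug will be considered as on-treatment, unless otherwise indicated by collection time".

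**The concern.** The SAP sets up a two-period safety framework, and its laboratory section then names a baseline that fits only one of the two periods. A programmer would normally let the specific rule in 12.2 override the general definitions in 7.6.1. SAP 12.3 on vital signs, by contrast, names no baseline and so leaves 7.6.1 to apply.

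If 12.2 is followed as written, the ferumoxytol-period laboratory change and shift tables implied by SAP 12 carry no information. Characterising MM-398 safety in the presence of ferumoxytol is a secondary objective. The ferumoxytol-period tables are the natural place to show what had already changed before MM-398 was given. A table of zeros could be misread as evidence that nothing changed.

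**Working it through.** No sample size or probability figure bears on this point. The check is to apply change = value − baseline to each scheduled laboratory value that falls in the ferumoxytol safety period.

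**Inputs**
- Baseline under SAP 12.2: last value before the first MM-398 dose.
- Baseline under SAP 7.6.1 for the ferumoxytol period: last value before ferumoxytol.
- Period (SAP 7.6.3): ferumoxytol dose to first MM-398 dose, or to 30 days if MM-398 is never given.
- Schedule (Protocol 8.2, Expansion Phase): CBC and serum chemistry at screening, within 7 days of the ferumoxytol dose; none on ferumoxytol Day 1 or Day 2; next at Cycle 1 Day 1. Urinalysis at screening and follow-up only.
- Interval (Protocol 4.2, SAP 3.1): Cycle 1 Day 1 within 7 days of ferumoxytol.
- Pre-dose requirement (Protocol 6.1.6.1): ANC and platelets before each MM-398 dose. No equivalent statement was found for other analytes.

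Let *s* be the screening value and *c* the Cycle 1 Day 1 value.

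**Ferumoxytol-period change by case**
1. *CBC or chemistry, c timed before the dose.* It is the only scheduled value in the period and also the 12.2 baseline. Under 12.2, change = c − c = 0 and the grade cannot shift. Under 7.6.1, change = c − s, a real post-ferumoxytol change.
2. *Ferumoxytol given, MM-398 never given.* There is no first MM-398 dose, so 12.2 supplies no baseline and change is undefined. Under 7.6.1, change = later value − s, provided a later value falls within 30 days.
3. *c recorded with a date only, on the dosing date.* SAP 7.1 and 7.6.3 assign it to MM-398. The ferumoxytol period then holds no scheduled value, and change is undefined under either baseline.
4. *Urinalysis in patients who go on to MM-398, or c missing.* The period holds no scheduled value. Change is undefined under either baseline.

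The baseline sentence causes cases 1 and 2, and using 7.6.1 repairs them. Case 3 comes from the date-only rule and case 4 from the visit schedule; changing the baseline alone repairs neither.

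**Grade 3 or higher listing.** With the 12.2 baseline, a value arising between ferumoxytol and MM-398 is not post-baseline in case 1. In case 2 there is no baseline for any value to follow. Such values reach the listing only if the investigator marks them clinically significant.

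**Secondary point: date-only values.** In case 3 the value counts as on MM-398. If that classification is carried through to baseline selection, the MM-398 baseline falls back to screening. The two candidate baselines can then be up to 7 + 7 = 14 days apart, and an abnormality present before dosing could be counted as an MM-398 shift. Whether this happens depends on whether collection times are recorded, which the documents do not show.

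**The case against.** The best defence is that 12.2 is correct for its main purpose. It repeats Protocol 10.7 and equals the MM-398 baseline in 7.6.1, and the stated objective concerns MM-398 in the presence of ferumoxytol. Read together, 12.2 supplies the MM-398 baseline and 7.6.1 covers the ferumoxytol period. The study is descriptive. The ferumoxytol risk that the protocol singles out, hypersensitivity, is followed as an adverse event of special interest rather than through blood counts or chemistry.

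Much of this stands. The pre-MM-398 baseline is right for MM-398 tables and should stay there. But 12.2 does not say it is limited to that period, and reading the sections together is exactly the edit needed. If 12.2 was meant for MM-398 only, the laboratory section still has to say which baseline the ferumoxytol tables use.

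Three stronger readings are tempting, and the documents do not support them.
- *That no laboratory effect after ferumoxytol could be seen at all.* Absolute values by visit put screening and Cycle 1 Day 1 side by side. Abnormality frequencies do not depend on the baseline, and medically relevant abnormalities are recorded as adverse events from ferumoxytol onward (Protocol 9.2).
- *That the MM-398 tables do mix baselines.* That is conditional on date-only samples, whose frequency is unknown, and on the period rule in 7.1 being applied to baseline selection.
- *That every patient in both phases is affected.* SAP 12 specifies safety summaries by cohort and overall for the Expansion Phase. The pilot schedule has been removed from this protocol version and cannot be checked.

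**Conclusion.** The conflict is real and should be corrected, but its reach is limited. In the Expansion Phase, about 30 patients, 12.2 as written makes scheduled ferumoxytol-period CBC and chemistry change and shift zero for a timed pre-dose Cycle 1 Day 1 value, and undefined for ferumoxytol-only patients. The grade 3 or higher listing shares the gap, subject to the investigator's clinical-significance flag. The number of ferumoxytol-only patients is not given and may be zero, although SAP 7.6.3 provides for them.

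MM-398-period change from a timed pre-dose value, absolute values, abnormality frequencies and adverse event tables are unaffected, and no primary endpoint is touched. The conclusion assumes that 12.2 is applied literally and that scheduled values are the ones summarised, as 12.2 states. An unscheduled value between ferumoxytol and Cycle 1 Day 1 could give a non-zero difference. The date-only issue is secondary and conditional on how collection times were recorded.

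**What to change.** In SAP 12.2, replace the single baseline with a statement that each safety period uses its own 7.6.1 baseline, also for deciding which values are post-baseline in the listing:
- **Ferumoxytol Safety Population:** change and shift from the last pre-ferumoxytol value to values before the first MM-398 dose, or to 30 days after ferumoxytol if MM-398 is never given.
- **MM-398 Safety Population:** change and shift from the last value before the first MM-398 dose.

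As a secondary edit, for the tests that Protocol 6.1.6.1 requires before dosing (ANC and platelets), treat a scheduled Cycle 1 Day 1 value with a date only as pre-dose, and say expressly that this overrides the date-only rules in 7.1 and 7.6.3. For other analytes use the recorded collection time. A default pre-dose label for those could turn a post-dose value into a baseline.

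The cost is SAP wording and one more set of laboratory tables from data already collected. The edit will not create ferumoxytol-period values for urinalysis, or where the Cycle 1 Day 1 sample is missing. A footnote should say that those gaps come from the visit schedule.

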12.3 Vital Signs

Vital signs data will be listed. In the vital signs listings, all values outside the normal ranges will be flagged to indicate whether they are above the upper limit of reference range (H) or below the lower limit of the reference range (L). Vital signs will be tabulated for the change from baseline by timepoint.

12.4 Electrocardiograms

Listings will be presented for ECG data. All ECG results of clinical significance, and those graded as CTCAE Grade 3 will be identified in the listing.

12.5 ECOG Performance Score

ECOG performance score will be summarized by study phase, study period, and study week.

12.6 Physical Examinations

Results of physical examinations will be listed by patient.

12.7 Pregnancies

Patients are to be discontinued from the study if they become pregnant. Pregnancy data will be shown in a data listing if applicable. No special analysis will be performed on the pregnancy data.

13 OTHER ANALYSES

13.1 Pharmacodynamic Marker Analysis

Post-hoc biomarker analysis may be performed. Details of analyses will be documented in a separate document.

14 Population Summary Conventions

- The population analyzed/displayed will be clearly and consistently identified on TLFs and will be identical in name to that identified in the protocol or SAP.

- Population sizes will be presented for each cohort as totals in the column header as (N=xxxx), where appropriate.
- All population summaries for continuous variables will include: n, mean, SD, minimum, and maximum. Other summaries (e.g. median, quartiles, 5%, 95% intervals, CV or %CV) may be used as appropriate.
- Summary statistic n values will denote the number of patients with non-missing values.
- Population summaries for categorical variables will include only categories where at least one patient had a response.
- In general, percentages will be rounded and reported to a single decimal point (xx.x%). Where percentages are reported as integers, percentages greater than 0% but <1% will be reported as <1% and percentages greater than 99% but <100% will be reported as >99%. A percentage of 100% will be reported as 100%, while 0% will be reported as a blank.
- Population summaries that include p-values will report the p-value to three decimal places with a leading zero (0.001). P-values <0.001 will be reported as <0.001.

16 APPENDIX A

From http://evs.nci.nih.gov/ftp1/CTCAE/CTCAE_4.03_2010-06-14_QuickReference_5x7.pdf

Parameter	Grade 1	Grade 2	Grade 3	Grade 4
Hemoglobin decreased	6.2 mmol/L - < LLN	4.9 mmol/L - <6.2 mmol/L	<4.9 mmol/L	
Hemoglobin increase	↑ in >0 – 2 g/dL above ULN or > BL if BL>ULN	↑ in >2 – 4 g/dL above ULN or > BL if BL>(ULN+2)	↑ in >4 g/dL above ULN or > BL if BL>(ULN+4)	
Lymphocyte decrease	0.8x10 ⁹ /L – <LLN	0.5x10 ⁹ /L – <0.8x10 ⁹ /L	0.2x10 ⁹ /L – <0.5x10 ⁹ /L	<0.2x10 ⁹ /L
Neutrophils decrease	1.5x10 ⁹ /L – <LLN	1.0x10 ⁹ /L – <1.5x10 ⁹ /L	0.5x10 ⁹ /L – <1.0x10 ⁹ /L	<0.5x10 ⁹ /L
Platelets decrease	75.0x10 ⁹ /L – <LLN	50.0x10 ⁹ /L – <75.0x10 ⁹ /L	25.0x10 ⁹ /L – <50.0x10 ⁹ /L	<25.0x10 ⁹ /L
WBC decrease	3.0x10 ⁹ /L – <LLN	2.0x10 ⁹ /L – <3.0x10 ⁹ /L	1.0x10 ⁹ /L – <2.0x10 ⁹ /L	<1.0x10 ⁹ /L
ALT increase	>1 ULN – 3xULN	>3xULN – 5xULN	>5xULN – 20xULN	>20xULN
Alkaline Phosphatase increase	>1 ULN – 2.5xULN	>2.5xULN – 5xULN	>5xULN – 20xULN	>20xULN
AST increase	>1 ULN – 3xULN	>3xULN – 5xULN	>5xULN – 20xULN	>20xULN
Total Bilirubin increase	>1 ULN – 1.5xULN	>1.5xULN – 3xULN	>3xULN – 10xULN	>10xULN
Creatinine increase	>1xBL – 1.5xBL or >1xULN – 1.5xULN	>1.5xBL – 3xBL or >1.5xULN – 3xULN	>3xBL – 6xBL or >3xULN – 6xULN	>6xBL or >6xULN

Parameter	Grade 1	Grade 2	Grade 3	Grade 4
Calcium increase	Corrected calcium*: >ULN – <2.9 mmol/L	> 2.9 mmol/L– 3.1 mmol/L	> 3.1 mmol/L– 3.4 mmol/L	>3.4 mmol/L
Calcium decrease	Corrected calcium*: 2.0 mmol/L – <LLN	1.75 mmol/L – <2.0 mmol/L	1.5 mmol/L – <1.75 mmol/L	<1.5 mmol/L
Albumin decrease	3 g/dL - <LLN	2 g/dL - < 3 g/dL	< 2 g/dL	
Magnesium decrease	0.5 mmol/L - <LLN	0.4 mmol/L - <0.5 mmol/L	0.3 mmol/L - <0.4 mmol/L	<0.3 mmol/L
Magnesium increase	>ULN – 1.23 mmol/L		>1.23 mmol/L – 3.30 mmol/L	>3.30 mmol/L
Potassium decrease	3.0 mmol/L - <LLN		2.5 mmol/L <3.0 mmol/L	<2.5 mmol/L
Potassium increase	>ULN – 5.5 mmol/L	>5.5 mmol/L – 6.0 mmol/L	>6.0 mmol/L – 7.0 mmol/L	>7.0 mmol/L
Glucose decrease	3.0 mmol/L - <LLN	2.2 mmol/L – 3.0 mmol/L	1.7 mmol/L - <2.2 mmol/L	<1.7 mmol/L
Sodium decrease	130 mmol/L - <LLN		120 mmol/L - <130 mmol/L	<120 mmol/L
Sodium increase	>ULN – 150 mmol/L	>150 mmol/L – 155 mmol/L	>155 mmol/L – 160 mmol/L	>160 mmol/L
Phosphate decrease	0.8 mmol/L - <LLN	0.6 mmol/L - <0.8 mmol/L	0.3 mmol/L - <0.6 mmol/L	<0.3 mmol/L
Uric Acid increase	>ULN – 0.59 mmol/L		>0.59 mmol/L	

*Corrected calcium (mmol/L) = Ca(mmol/L) + 0.02[40(g/L) – albumin(g/L)]; refer to calcium (mmol/L) lab normal range for LLN and ULN values.
